21.2 Quality Control

The Principal Investigator (or designee) will keep accurate records to ensure that the conduct of the study is fully documented. The investigator will ensure that all CRFs and participant study files are legible and complete for every participant. The Principal Investigator (or designee), through the use of an internal Quality Management Plan, appropriate site quality control, and quality assurance monitoring staff, will be responsible for the regular review of the conduct of the study for verifying adherence to the protocol, and for confirming the completeness, consistency, and accuracy of all documented data and accuracy of source documentation verification. All charts will be 100% Quality Controlled. The first five volunteers enrolled will receive a 100% Quality Assurance review. The reports of the internal site monitor will be submitted to the Principal Investigator (or designee). The RedCap data entry system will include checks for data that are outside feasible limits (e.g., dates that are in the future) or skipped answers.

21.3 Data and specimen handling

All de-identified samples will be stored at the Hope Clinic by laboratory staff using only the study number, PTID, date of visit, and visit number. Data regarding safety and adverse events will be maintained at the Hope Clinic of Emory University. Data from immunological assays and gene expression analysis (RNA sequencing) will be linked to PTID, maintained by [REDACTED] laboratory at Stanford University, and accessible to investigators and laboratory staff. Laboratory

data and demographic data may be linked by PTID for statistical analysis by investigators or collaborators (e.g., to control for age); however, PTID will not be published nor will the gene expression (RNA sequencing) data be linked to demographic data in order to protect participant privacy and prevent the discovery of participant identity.

Specimens and demographic data linked by PTID will be stored indefinitely, but all personal identifiable information (PII) and PII/PTID links will be destroyed once the laboratory analysis associated with this protocol is complete and the last manuscript associated with this protocol has been published.

Study investigators and personnel will maintain the highest degree of confidentiality for the clinical and research information obtained from the participants. Medical and research records will be maintained in the strictest confidence. However, as a part of the quality assurance and legal responsibilities of a clinical study, investigators will permit authorized representatives of regulatory authorities to examine (and when required by applicable law, to copy) clinical records for the purpose of quality assurance reviews and evaluations of study safety and progress. Unless required by laws that permit copying of records, only the PTID associated with documents or with other participant data may be copied (and all personally identifying information will be removed). Authorized representatives described above are bound to maintain the strict confidentiality of medical and research information that is linked to identify individuals.

Blood tubes will be labeled at the Hope Clinic with a unique identifier and will be transported to the lab at the Hope Clinic in EHSO-approved transport containers.

22. Plans to Monitor the Data to Ensure Safety of Participants and Data Integrity

More than minimal risk – Continue below.

Review our [Data and Safety Monitoring Questionnaire](#) and insert the relevant monitoring table at the end of this section. Also upload the completed questionnaire in the “Basic Study Information” smartform section in eIRB, question #8, as a separate document.

Mark the risk categorization, as determined by the Data and Safety Monitoring Questionnaire, that applies to your study below:

Select one of the following (do not delete this table; review the guidance document for definitions):	
 Medium Complexity	
 High Complexity Category A	
 High Complexity Category B	

If choosing this category for a study under an IND or IDE because you believe the study intervention does not significantly impact morbidity or mortality, please provide your rationale:

DSMP Requirement	How this Requirement is Met	Frequency	Responsible Party(ies)
Real-time review of participant data during initial data collection.	100% QC review by CRC/CRN and peer review within 3 business days. QM will review first 5 participants in real time.	Expectation is that this happens every time you obtain information.	CRC/CRNs QM Manager/Team
Site Monitoring at pre-determined intervals: The Principal Investigator has a responsibility to ensure that the study is following all aspects of the protocol.	There should be a standard operating procedure to review data (whether a sample or 100%) at pre-determined intervals to ensure that there is adequate documentation of critical elements such as eligibility criteria. Monitoring is required at the following timepoints (but may be done more frequently): 
 study initiation at least every six months while participants are receiving intervention and annually while participants are in follow-up 	At a minimum, a review is required annually when no one has been enrolled or the study is in long term follow up. Additional risk-based interim monitoring may be required at least once every 12-24 weeks based on the site activity, to include the possibility of remote monitoring. A longer frequency could be acceptable with justification about risk to participants.	Delegate a responsible party for each requirement below. Self-assessment is acceptable*. Self-assessment: a process for self-assessment of protocol compliance and data integrity which can be part of an overall DSMP. See CTAC's self-assessment tool on their webpage.
100% review of regulatory files	Site QM will conduct 100% review of reg files at the beginning and at close-out visit at a minimum.	Reviewed at a minimum of first and close-out visits	QM Manager/Team Regulatory Team

Systems Biological Assessment of Statin Effect on Vaccine Responses

100% review of consent forms	CRC/CRNs will perform peer review in real time for 100% of ICFs. QM will conduct 100% review of ICFs.		CRC/CRNs QM Manager/Team
Review of credentials, training records, the delegation of responsibility logs (if applicable)	QM and Regulatory Team will conduct 100% review of credentials/training records/DoA files quarterly at a minimum.		QM Manager/Team Regulatory Team
Comparison of case report forms (CRF) to source documentation for accuracy and completion	QM will conduct 100% review for first 5 participants in real time and on a monthly basis throughout the study.		QM Manager/Team
Review of documentation of all adverse events	SAEs will be reviewed by PI and designee and peer reviewed by CRC/CRNs and verified by QM team and evaluated by the ISM and Emory IRB.		CRC/CRNs QM Manager/Team
Monitoring of critical data points (eligibility, study endpoints, etc.)	QM will conduct 100% review for first 5 participants in real time and on a monthly basis throughout the study.		QM Manager/Team
Laboratory review of processing and storage of specimens	Peer review of sample log in done in real time and answering queries regularly	Reviewed at first and close-out visits and at least biannually	Lab Manager or designee
Assessment of laboratory specimens stored locally	Peer review of sample log in done in real time and answering queries regularly- shipment done within 2 weeks		Lab Manager or designee
Test article accountability review	Day to day and monthly per IDS pharmacist	Reviewed at first and close-out visits and at least biannually	Research Pharmacist
Accountability logs, dispensing records, and other participant records	Monthly per IDS pharmacist	At least biannually	Research Pharmacist

For FDA regulated studies, the following requirements apply:		Timing, frequency, and intensity of monitoring	
Monitoring methods (may include centralized, on-site, and self-assessment)	Monitoring visits will include, but are not limited to, review of regulatory files, accountability records, electronic case report forms (eCRFs), ICFs, medical and laboratory reports, site study intervention storage records, training records, and protocol and GCP compliance. Site monitors will have access to each participating site, study staff and all study documentation according to the Hope Clinic CQMP. Study monitors will meet with all participating site PIs to discuss any problems and outstanding issues and will document site visit findings and discussion.	Monitoring visits are expected to occur monthly or bimonthly. Details of clinical site monitoring are documented in a clinical monitoring plan (CMP). The CMP describes in detail who will conduct the monitoring, at what frequency monitoring will be done, at what level of detail monitoring will be performed, and the distribution of monitoring reports.	Monitoring for this study will be performed by the QM team.

*For international studies, you are required to engage a CRO that is working in the site country and/or to consult with Emory's legal counsel regarding compliance with the country's clinical research regulations.

22.1 Study Oversight

The Principal Investigator and the research team (co-Investigators, research nurses, study coordinators, and data managers) are responsible for identifying adverse events. Adverse events will be reviewed regularly by the research team.

22.2 Adverse Events

This section defines the types of adverse events that may occur, and outlines the procedures for appropriate adverse event collecting, grading, recording, and reporting.

Information in this section complies with 21CFR 312; ICH Guideline E2A: Clinical Safety Data Management: Definitions and Standards for Expedited Reporting and Good Clinical Practice; and applies the standards set forth in the National Cancer Institute (NCI), Common Terminology Criteria for Adverse Events Version 5.0 [Published: November 27, 2017; <http://evs.nci.nih.gov/ftp1/CTCAE/About.html>]. These criteria have been reviewed by the study investigators and have been determined to be appropriate for this study population.

22.2.1 Safety Reporting

22.2.2 Adverse Events

An adverse event (also referred to as an adverse experience) can be any unfavorable and unintended sign, symptom, or disease temporally associated with the use of the procedure, without any judgment about causality.

After vaccination, the following adverse events in the indicated intervals may be reported to Vaccine Adverse Event Reporting System (VAERS).

- Anaphylaxis or anaphylactic shock (7 days)
- Shoulder Injury Related to Vaccine Administration (7 days)
- Vasovagal syncope (7 days)
- Any acute complication or sequelae (including death) of above events (interval - not applicable)
- Events described in manufacturer's package insert as contraindications to additional doses of vaccine: hypersensitivity, including severe allergic reactions after previous dose of influenza vaccine

22.2.3 Suspected Adverse Reaction (SAR)

Suspected adverse reaction means any adverse event for which there is a reasonable possibility that the drug or procedure caused the adverse event. Suspected adverse reaction implies a lesser degree of certainty about causality than adverse reaction, which means any adverse event caused by a drug.

SARs after vaccine administration may include:

- Local reactions: injection site redness, injection site swelling, pain at the site of injection, itching of the skin at the injection site.
- Systemic reactions: headache, fever, nausea, dizziness.

SARs after phlebotomy may include:

- Local reactions: pain at the site of venipuncture, bruising at the site of venipuncture, infection at the site of venipuncture
- Systemic reactions: lightheadedness or fainting

22.2.4 Serious Adverse Event (SAE) or Serious Suspected Adverse Reaction

An adverse event or suspected adverse reaction is considered "serious" if, in the view of the investigator, it results in any of the following outcomes:

- Death
- A life-threatening adverse event
- Inpatient hospitalization or prolongation of existing hospitalization
- A persistent or significant incapacity or substantial disruption of the ability to conduct normal life functions
- A congenital anomaly/birth defect

Important medical events that may not result in death, be life-threatening, or require hospitalization may be considered serious when, based upon appropriate medical judgment, they may jeopardize the participant and may require medical or surgical intervention to prevent one of the outcomes listed in this definition. Serious adverse events will be reported and recorded for the entire duration of the study.

An adverse event or suspected adverse reaction is considered “life-threatening” if, in the view of the investigator, its occurrence places the patient or participant at immediate risk of death. It does not include an adverse event or suspected adverse reaction that, had it occurred in a more severe form, might have caused death.

Any serious adverse event (for duration of study) will be recorded and reported within 24 hours to ISM.

22.2.5 Unexpected Adverse Event or Unexpected Suspected Adverse Reaction

An adverse event or suspected adverse reaction is considered “unexpected” if it is not listed in the Summary of Product Characteristics or is not listed at the specificity or severity that has been observed; or, if the Summary of Product Characteristics is not required or available, is not consistent with the risk information described in the general investigational plan or elsewhere in the current application, as amended.

22.2.6 Independent Safety Monitoring

The ISM, is a physician with relevant expertise in clinical studies whose primary responsibility will be to provide independent safety monitoring in a timely fashion and to provide recommendations regarding the safe continuation of this study.

The ISM will evaluate safety data generated from study participants against the known safety profile of the study product or study procedure to assess for possible changes to the overall risk of the study.

The ISM will communicate with the Principal Investigator as needed. The study has provisions for a back-up ISM to ensure that independent safety monitoring happens at all times during the study.

22.2.7 Collecting and Recording Adverse Events and Pregnancy

Adverse events may be identified during this study through any of these methods:

- Examination of the participant during study visits.
- Questioning the participant during study visits.
- Receiving a safety contact from the participant at any time during the study

Note: participants will be asked to call the site if they develop any of the following:

- Any adverse event that limits self-care activities of daily living (e.g. bathing, dressing and undressing, feeding self, using the toilet, taking medications, and not bed ridden) even if he/she decides not to seek medical care

Reactogenicity of any grade is collected for 7 days after vaccination.

Serious adverse events will be recorded if they occur at any time during the study.

A complete recording of safety events in the CRF will include event term; date(s) of onset and resolution/stabilization; assessment of severity; relationship to procedures/intervention(s); expectedness; determination of whether the AE qualifies as serious or non-serious; treatment required; action taken with study participation; and outcome. AEs qualifying as serious also require a narrative of the event. Updates in safety events will be recorded as additional information becomes available.

Information on pregnancies will be collected from the time a participant signs the consent until the participant completes study participation. If a participant becomes pregnant after study entry, the investigator will discuss with the participant and/or the treating provider the known possible risks to the fetus. Participants becoming pregnant after study entry will be withdrawn from the study and followed until the end of the pregnancy for safety. A pregnancy resulting in congenital anomaly/birth defect will be considered a SAE. Any premature termination of the pregnancy will also be reported and assessed as an SAE as needed.

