Study recruiters/coordinators will contact potential volunteers once identified and tell them about the study and see if he/she is interested. If the potential subject is interested, the recruiter will obtain an oral consent and prescreen them for the study using an IRB-approved screening checklist. Qualified subjects will be scheduled to come into the clinic and be fully consented and proceed with screening/enrollment.

16. Withdrawal of Participants

Participants may voluntarily withdraw their consent from all future study activities including follow up at any time without penalty or loss of benefits to which they are otherwise entitled.

Participants may be terminated from the study prior to study completion for reasons that might include, but are not limited to, those listed below. The investigator will inform the participant that all data acquired prior to termination will be included in the study analysis unless participant withdraws consent.

16.1 Participant no longer meets eligibility criteria.

16.2 The participant is considered by the PI to be “lost to follow-up” (i.e., no further followup is possible because attempts to reestablish contact with the subject have failed).

16.3 The participant dies.

16.4 As deemed necessary by the PI or designee for noncompliance of any nature.

16.5 The participant becomes pregnant.

16.6 If the study is prematurely terminated by the sponsor or the investigator for any reason, the investigator will promptly inform the study participants and assure appropriate follow-up, as necessary. The investigator will provide a detailed written explanation of the termination to the IRB.

Participants with early termination status (before Day 8) are replaced as needed to preserve adequate sample size for the primary endpoint analysis.

17. Continuation of treatment

- Following initiation of statin therapy, participants randomized to the statin therapy+QIV group will: Continue receiving the study drug as planned if they experience grade 1 diarrhea or grade 1 elevation in CPK(>ULN - 2.5 x ULN) or LFTs (>ULN - 3.0 x ULN).

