- Temporarily halt receipt of statin therapy for three to 7 days and receive a new set of safety labs (CPK; LFTs) if they experience a grade 2 elevation in CPK (>2.5 x ULN - 5 x ULN) or LFTs (>3.0 - 5.0 x ULN) and without alternative etiology. If afterwards the labs are graded 1 or within normal limits, the participant may restart the statin therapy. If the labs do not trend to grade 1, the drug will be halted and the participant will be followed for safety and not vaccination if prior to D1.
- Permanently halt receipt of statin therapy if they experience a grade 3 elevation in CPK (>5 x ULN - 10 x ULN) or LFTs (>5.0 - 20.0 x ULN) after starting ST.
- The same rules apply to diarrhea and myalgias and other symptoms related to statin.

18. Risk to Participants

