22.3 Grading and Attribution of Adverse Events

22.3.1 Grading Criteria

Adverse events will be graded according to the criteria set forth in the National Cancer Institute's Common Terminology Criteria for Adverse Events Version 5.0 [November 27, 2017; <http://evs.nci.nih.gov/ftp1/CTCAE/About.html>] This document (referred to herein as the NCI-CTCAE manual) provides a common language to describe levels of severity, to analyze and interpret data, and to articulate the clinical significance of all adverse events. All adverse events whether or not listed in the NCI-CTCAE will be graded on a scale from 1 to 5 according to the following standards in the NCI-CTCAE manual (A semicolon indicates 'or' within the description of the grade):

- Grade 1 Mild; asymptomatic or mild symptoms; clinical or diagnostic observations only; intervention not indicated.
- Grade 2 Moderate; minimal, local or noninvasive intervention indicated; limiting age-appropriate instrumental ADL*.
- Grade 3 Severe or medically significant but not immediately life-threatening; hospitalization or prolongation of hospitalization indicated; disabling; limiting self-care ADL**.
- Grade 4 Life-threatening consequences; urgent intervention indicated.
- Grade 5 Death related to AE.

*Instrumental Activities of Daily Living (ADL) refer to preparing meals, shopping for groceries or clothes, using the telephone, managing money, etc.

**Self-care Activities of Daily Living (ADL) refer to bathing, dressing and undressing, feeding self, using the toilet, taking medications, and not bedridden.

Not all Grades are appropriate for all AEs; therefore, some AEs are listed with fewer than five options for Grade selection.

Anaphylaxis is a disorder characterized by an acute inflammatory reaction resulting from the release of histamine and histamine-like substances from mast cells, causing a hypersensitivity immune response. Clinically, it presents with breathing difficulty, dizziness, hypotension, cyanosis and loss of consciousness and may lead to death. Severity grading of anaphylaxis as per the NCI-CTCAE manual is as follows:

- Grade 1= not applicable
- Grade 2= not applicable
- Grade 3= Symptomatic bronchospasm, with or without urticaria; parenteral intervention indicated; allergy-related edema/angioedema; hypotension
- Grade 4= Life-threatening consequences; urgent intervention indicated
- Grade 5= Death

Severity grading of AEs of laboratory abnormalities will be assessed as per the NCI-CTCAE manual.

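### Minor: the only call-in trigger that maps to a grade (22.2.7) sits at grade 3, the permanent-halt level, while Section 17 already holds the statin and retests at grade 2

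*Combined protocol and SAP*

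**What the plan says.** **When participants should call.** Section 22.2.7 introduces a list of reasons to call the site, and one item follows: "Any adverse event that limits self-care activities of daily living". It applies to all participants, whether or not they seek medical care. For the statin arm, Section 5.2 adds an instruction to contact staff at once about symptoms that concern the participant. It gives no severity level or examples and does not mention Section 17. Section 6.2 has staff explain common side-effects when the drug is handed over.

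**What the grades mean.** Section 22.3.1 defines "Grade 2 Moderate; minimal, local or noninvasive intervention indicated; limiting age-appropriate instrumental ADL" and "Grade 3 Severe or medically significant but not immediately life-threatening; hospitalization or prolongation of hospitalization indicated; disabling; limiting self-care ADL".

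**What the protocol does at each grade (Section 17).**
- Grade 1: "Continue receiving the study drug as planned if they experience grade 1 diarrhea", and likewise for grade 1 CPK or liver test elevations.
- Grade 2 laboratory elevation: "Temporarily halt receipt of statin therapy for three to 7 days and receive a new set of safety labs". If the repeat values do not come down to grade 1, "the drug will be halted and the participant will be followed for safety and not vaccination if prior to D1".
- Grade 3: "Permanently halt receipt of statin therapy if they experience a grade 3 elevation in CPK" or in liver tests.
- Symptoms: "The same rules apply to diarrhea and myalgias and other symptoms related to statin".

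**Staff-initiated checks.** There is one phone call 15 days after the first dose (6.3). AEs are recorded at the visits to D29 (6.5, Appendix A). Appendix A places the statin safety labs at screening, D1 and D29, so the only ones on drug are at D1 and D29. The memory aid covers the 7 days after vaccination (6.4).

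**The concern.** The call-in level and the action level do not match. A participant who follows 22.2.7 to the letter first calls when the event already meets the criterion for stopping the drug permanently. The milder step, a short hold and a retest, is then passed over. Section 22.4 suspends study procedures after two cases of severe myalgia. Since 22.3.1 describes grade 3 as severe, that same first call could concern an event that counts toward suspension.

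At stake is the safety of healthy volunteers who take 80 mg daily without a therapeutic need. No safety labs are scheduled between the first dose and D1. In that month, apart from the single phone call, a hold starts only if the participant makes contact. Timing before D1 also matters because Section 17 makes vaccination depend on the retest.

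**Working it through.** The plan gives no figure to reproduce. The check compares texts, then looks at the calendar.

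**1. Levels side by side**

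| Level | Meaning in 22.3.1 | Action in Section 17 | Call-in text that reaches it |
|---|---|---|---|
| Grade 1 | mild | continue | 5.2, if the participant is concerned |
| Grade 2 | minor intervention, or instrumental ADL limited | hold 3 to 7 days, new CPK and liver tests | 5.2, if the participant is concerned |
| Grade 3 | includes self-care ADL limited | permanent halt | 22.2.7 and 5.2 |

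The 22.2.7 trigger is one grade above the first action and equal to the last. Two limits apply. Section 17's cut-offs are written for laboratory values and reach symptoms through one sentence. And no call-in rule can detect a silent laboratory elevation.

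**2. Intervals on drug without a scheduled contact**

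Inputs: statin start D-31 to D-29; call 15 days later; visits D1, D2, D4, D8, D15, D29. The range allows for counting with or without a day 0.
- Start to D1: 29 to 32 days.
- Start to call: 15 days.
- Call to D1: 29 − 15 = 14 to 32 − 15 = 17 days.
- D15 to D29: 14 days nominal. With windows of ±2 and ±3 days, 9 to 19.
- Start to D29: 29 + 28 = 57 to 32 + 28 = 60 days.
- Share of dosing days in these three intervals: (29 + 14)/57 = 75.4% to (32 + 14)/60 = 76.7%.
- Share covered by the memory aid: 7/60 = 11.7% to 7/57 = 12.3%, none of it before D1.

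**3. Timing before vaccination**

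A symptom raised at the phone call leaves 14 to 17 days, enough for a 7-day hold. The interval that matters is call to D1. Assume onsets spread evenly over it and reported at once:
- 3-day hold finished by D1: (14 − 3)/14 = 79% to (17 − 3)/17 = 82%.
- 7-day hold finished by D1: (14 − 7)/14 = 50% to (17 − 7)/17 = 59%.
- First reported at D1: 0%, unless D1 is moved. Appendix A allows out-of-window visits at the investigator's discretion.

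**4. How many participants?**

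Section 18.1 gives 3 to 8% for muscle symptoms and 4 to 14% for a group that includes diarrhea, at any grade and with no exposure time. Applied to 30 participants over this course (an assumption), that is 0.9 to 2.4 and 1.2 to 4.2 events. The documents give neither the grade 2 share nor the proportion who would call under 5.2. Taking 10 to 50% as grade 2 and 25 to 75% as not calling, both assumed:
- Low: (0.09 + 0.12) × 0.754 × 0.25 = 0.04.
- High: (1.2 + 2.1) × 0.767 × 0.75 = 1.9.

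The ends differ almost 50-fold, driven largely by the assumed shares. This shows only that the number is small.

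**The case against.** The strongest reply is that the plan already handles this. Section 5.2 is the statin-specific instruction and has no severity floor. The 22.2.7 item is a level at which everyone must call, not a threshold for statin symptoms. Grading is staff work, so a participant instruction need not cite Section 17. Section 22.2.7 also accepts a safety contact from a participant at any time. Staff ask about drug complications at the phone call and can bring the participant in. The consent form and the handout given with the drug are not in the reviewed documents and may already say more.

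Most of this stands, and it rules out stronger readings. A reader might infer that participants are told to stay silent below grade 3, or that grade 2 events go unrecorded. The documents do not support either: 5.2 invites earlier contact, and AEs are recorded at every visit to D29, so the issue is delay. A reader might also infer harm to the safety endpoint. A report delayed to the next visit is still recorded, so the documents do not show that either. Nor can it be claimed that fewer than one participant would be affected. That holds only if diarrhea is left out; with it, the illustrative upper end is 1.9.

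What the reply does not remove is that 5.2 leaves the threshold to the participant, while the only stated level is one grade above the protocol's own first action.

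**Conclusion.** The point holds as a minor, inexpensive safety improvement. The mismatch between 22.2.7, 22.3.1 and Section 17 is in the text and needs no assumption beyond reading Section 17's symptom sentence as applying the same grade levels. Its consequence is a possible delay of up to about two weeks in three intervals: start to call, call to D1, and D15 to D29. It concerns a grade 2 symptom that the participant does not find worrying. In the last interval, the delay can mean finishing the course on a dose that Section 17 would have held. The number affected cannot be derived from the documents and is likely to be very few of 30. If the consent form or the dispensing instructions already set a grade 2 trigger, only the protocol text needs to match them.

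**What to change.** Keep 5.2 as it is, and keep the self-care trigger in 22.2.7 as the minimum for all participants. Add one sentence to both sections: while on drug, statin-arm participants should call promptly about muscle pain, tenderness or weakness, diarrhea, or another possible statin symptom, if it needs treatment or limits usual activities such as shopping or preparing meals. Staff then grade it and apply Section 17. This covers both parts of the grade 2 definition.

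Exclude injection-site pain and expected muscle aches in the 7 days after vaccination, unless they meet the self-care trigger or persist beyond Day 8. The memory aid and the D2, D4 and D8 visits already capture these. Without the exclusion, and without the grade 2 qualifier, the trigger would draw in ordinary vaccine reactions. Section 18.1 puts vaccine reactions, muscle aches among them, at 10 to 25% of adults. If that is taken as the rate of muscle pain, it is 3 to 7.5 of 30.

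Add a CRF field recording whether each AE came from a call or a scheduled contact.

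Cost: a few calls, some unscheduled visits and repeat CPK and liver tests. For muscle symptoms and diarrhea, with the same assumed 10 to 50% grade 2 share, there would be 0.2 to 3.3 calls. At Section 20's $20 per call plus $50 per unscheduled visit, that is 0.21 × $70 = $15 to 3.3 × $70 = $231, before laboratory costs, which the documents do not give. Other statin symptoms would add to this, and people who would call under 5.2 anyway would reduce it. The other cost is slightly fuller AE ascertainment in the statin arm of an open-label comparison, which the source field makes visible.
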